#### Abscess

• The proportion of participants who achieved complete elimination of abscesses at Week 12 and Week 16 will be compared between each of the bermekimab groups and the placebo group among participants who had any abscess at baseline.

- The change from baseline in number of abscesses at Week 12 and Week 16 will be compared between each of the bermekimab groups and the placebo group respectively.
- The change from baseline in number of abscesses will be summarized by treatment group over time.

#### Fistulas

- The proportion of participants who achieved complete elimination of draining fistulas at Week 12 and Week 16 will be compared between each of the bermekimab groups and the placebo group among those with draining fistulas at baseline.
- The change from baseline in number of draining fistulas at Week 12 and Week 16 will be compared between each of the bermekimab groups and the placebo group respectively.
- The change from baseline in number of draining fistulas and non-draining fistula will be summarized by treatment group over time.

#### Inflammatory Nodules non-inflammatory Nodules

- The proportion of participants who achieved complete elimination of inflammatory nodules at Week 12 and Week 16 will be compared between each of the bermekimab groups and the placebo group among those with inflammatory nodules at baseline.
- The change from baseline in number of inflammatory nodules at Week 12 and Week 16 will be compared between each of the bermekimab groups and the placebo group respectively.
- The change from baseline in number of inflammatory nodules will be summarized by treatment group over time.
- The change from baseline in number of non-inflammatory nodules will be summarized by treatment group over time.

# 5.4.3.3. Modified Hidradenitis Suppurativa Score (mHSS) (Modified Sartorius Score)

## 5.4.3.3.1. Definition

The Sartorius Scale is used to quantify the severity of HS. Points are awarded for 12 body areas (left and right axillae, left and right sub/inframammary areas, intermammary area, left and right buttocks, left and right inguino-crural folds, perianal area, perineal area, and other): points were awarded for nodules (2 points for each); abscesses (4 points); fistulas (4 points); scars (1 point); other findings (1 point); and longest distance between two lesions (2-6 points, 0 if no lesions); and if lesions are separated by normal skin (yes-0 points; no-6 points). The total Sartorius score is the sum of the 12 regional scores.

#### 5.4.3.3.2. Analysis Related to Modified Hidradenitis Suppurativa Score (mHSS)

- The change from baseline in modified Hidradenitis Suppurativa score at Week 12 and Week 16 will be compared between each of the bermekimab groups and the placebo group respectively.
- The change from baseline in modified Hidradenitis Suppurativa score will be summarized by treatment group over time.

## 5.4.3.4.2. Analysis Related to HS-PGA

- The proportion of participants who achieved HS-PGA of clear (0), clear (0) or minimal (1) or HS-PGA score of mild or better (≤ 2) with at least a 2-grade improvement relative to baseline at Week 12 and Week 16 will be compared between each of the bermekimab groups and the placebo group respectively.
- The proportion of participants with 1-grade and 2-grade improvement in HS-PGA scores from baseline will be summarized over time respectively.
- The proportion of participants who achieved HS-PGA of clear (0), clear (0) or minimal (1) or HS-PGA score of mild or better (≤ 2) with at least a 2-grade improvement relative to baseline will be summarized over time by treatment group.

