3.1 STUDY ENDPOINTS

Primary Endpoint:

 Proportion of subjects achieving Hidradenitis Suppurativa Clinical Response (HiSCR) at week 12

Secondary Endpoints:

- Change from baseline to week 32 in Numeric Rating Scale for Pain & Itch (NRS Pain & Itch) score
- Change from baseline to week 16 in Numeric Rating Scale for Pain & Itch (NRS Pain & Itch) score
- Change from baseline to week 12 in Numeric Rating Scale for Pain & Itch (NRS Pain & Itch) score

- Change from baseline to week 8 in Numeric Rating Scale for Pain & Itch (NRS Pain & Itch) score
- Proportion of subjects achieving Hidradenitis Suppurativa Clinical Response (HiSCR) at week 32
- Proportion of subjects achieving Hidradenitis Suppurativa Clinical Response (HiSCR) at week 16
- Change in Modified Hidradenitis Suppurativa Score (mHSS), Hidradenitis Suppurativa Physician's Global Assessment (HS-PGA) and Hurley Stage from baseline to week 32
- Change in Modified Hidradenitis Suppurativa Score (mHSS), Hidradenitis Suppurativa Physician's Global Assessment (HS-PGA) and Hurley Stage from baseline to week 16
- Change in Modified Hidradenitis Suppurativa Score (mHSS), Hidradenitis Suppurativa Physician's Global Assessment (HS-PGA) and Hurley Stage from baseline to week 12
- Change in patient reported outcomes from baseline to week 32, including: Hospital Anxiety and Depression Scale (HADS), Dermatology Life Quality Index (DLQI), Health Status Questionnaire (EQ-5D-3L), Patient Global Impression of Change (PGI-c), Patient Global Impression of Severity (PGI-s) and Hidradenitis Suppurativa Symptom Diary (HSSD) HS related Pain Symptom Score in the past 24 hours and total symptom score
- Change in patient reported outcomes from baseline to week 16, including: Hospital Anxiety and Depression Scale (HADS), Dermatology Life Quality Index (DLQI), Health Status Questionnaire (EQ-5D-3L), Patient Global Impression of Change (PGI-c), Patient Global Impression of Severity (PGI-s) and Hidradenitis Suppurativa Symptom Diary (HSSD) HS related Pain Symptom Score in the past 24 hours and total symptom score
- Change in patient reported outcomes from baseline to week 12, including: Hospital Anxiety and Depression Scale (HADS), Dermatology Life Quality Index (DLQI), Health Status Questionnaire (EQ-5D-3L), Patient Global Impression of Change (PGI-c), Patient Global Impression of Severity (PGI-s) and Hidradenitis Suppurativa Symptom Diary (HSSD) HS related Pain Symptom Score in the past 24 hours and total symptom score

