10.1 DETERMINATION OF SAMPLE SIZE

The primary efficacy endpoint is percent of patients who have a positive HiSCR score (achiever) at week 12. The positive HiSCR score is defined as $a \ge 50\%$ reduction in inflammatory lesion AN count (sum of abscesses and inflammatory nodules), and no increase in abscesses or draining fistulas in HS compared with the lesions counted at baseline. The sample size is calculated for the bermekimab weekly injection group (Treatment Arm 1) versus placebo group (Treatment Arm 3) comparison (the primary comparison).

Assuming a positive HiSCR score is achieved in 60% of intent-to-treat (ITT) patients treated in the bermekimab weekly injection group (Treatment Arm 1) versus 30% in placebo treated patients (Treatment Arm 3), then, for a randomization ratio of 1:1:1, a sample size of 126 patients (42 in each treatment group) is required for approximately 80% power at a 0.05 significance level using a 2-sided Pearson chi-square test. In order to account for possible dropouts and to provide adequate safety data, approximately 150 patients will be randomized and treated.

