10.5.3.2 Secondary Efficacy Analyses

Secondary efficacy endpoints (NRS pain & itch, HiSCR, mHSS, HS-PGA, PGA-ISD, HADS, DLQI, EQ-5D-3L, PGI-c, PGI-s, HiSQOL, IHS4 and HSSD) will be summarized using descriptive statistics on actual and change from baseline values over time by treatment group. The 95% CI of the mean change from baseline will be provided. The change from baseline in these endpoints at each week will be analyzed using a restricted maximum likelihood (REML)-based mixed model for repeated measures (MMRM) with fixed effects for treatment, week, stratification factors (prior anti-tumor necrosis factor, IL-17 inhibitor therapy

use (yes/no) and Hurley Stage (II/III)), baseline score, baseline score by week interaction, and the treatmentby-week interaction, if applicable. The impact of the stratification factors will also be assessed. Hurley Stage, PGI-c, and PGI-s categories will also be summarized descriptively.

Responder analyses will also be performed for select efficacy variables including NRS pain (categorized as \geq 30% reduction on pain score among patients with baseline score of \geq 3), NRS itch (3 point improvement in patients with \geq 3 itch score at baseline as well as 4 point improvement in patient with \geq 4 itch score at baseline) at each week. The number and percentage of patients who meet these criteria will be summarized by treatment group. Additional responder analyses may be performed for other efficacy variables. Full details will be provided in the statistical analysis plan.

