## 5.4.1. Analysis Methods

The secondary efficacy analyses outlined in the following sections in general will be carried out at key endpoints (Week 12 and Week 16) and over time.

Most of the secondary efficacy analyses described in sections below will be based on FAS. For participants randomized to placebo, only participants who crossed over to receive bermekimab at Week 16 will be included in the efficacy summaries for the visits after Week 16. All statistical testing will be performed at the 2-sided 0.05 significance level. Nominal p-values will be presented.

## 5.4.1.1. At Week 12 and Week 16

For continuous endpoints where longitudinal data were collected prior to the analysis visits; treatment comparisons will be performed using Mixed-Effect Model Repeated Measure (MMRM) model, with fixed effects for treatment, week, stratification factors (prior biologic use (yes/no), screening Hurley stage (II/III)) when sample size in each category of the stratification variables is permitted, and baseline value in the model. The MMRM model will also include prior biologic use by visit, screening Hurley stage by visit, and baseline value by visit interaction and the treatment-by-week interaction as additional explanatory factors.

The model will be performed based on all available data from the 3 treatment groups through Week 16. The treatment difference between a guselkumab group and the placebo group will be estimated by the difference in the least squares means (LSmeans). The 95% CIs for the differences in LSmeans and p-values will be calculated.

For binary response endpoints treatment comparisons will be performed using a Cochran-Mantel-Haenszel (CMH) test stratified by the prior biologic use (yes/no) and screening Hurley stage (II/III) with missing data imputed with Non-Responder Imputation (NRI) defined in Section 5.2.2.

For the PRO endpoints with ordinal scale, the Cochran-Mantel-Haenszel (CMH) mean scores test stratified by prior biologic use (yes/no) and screening Hurley stage (II/III) will be used to compare bermekimab and placebo. The distribution of ordinal scale category will also be provided.

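### The SAP drops the protocol's change-from-baseline comparison for HS-PGA and tests only responder cuts, without giving a reason

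*SAP*

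**What the plan says.** - **Endpoint (Protocol 3.1).** Change from baseline is listed as a secondary endpoint for HS-PGA at Weeks 12, 16 and 32. The Week 12 entry ends "HS-PGA) and Hurley Stage from baseline to week 12".
- **Method (Protocol 10.5.3.2).** HS-PGA is in the list of secondary endpoints, and the section then states: "The change from baseline in these endpoints at each week will be analyzed using a restricted maximum likelihood (REML)-based mixed model for repeated measures". Hurley Stage, PGI-c and PGI-s are singled out for extra category summaries; HS-PGA is not.
- **SAP comparison (5.4.3.4.2).** The only between-arm comparisons are of proportions at Weeks 12 and 16: grade 0; grade 0 or 1; or grade 2 or lower "with at least a 2-grade improvement relative to baseline at Week 12 and Week 16 will be compared between each of the bermekimab groups", always against placebo. The proportions with one-grade and two-grade improvement are summarised over time without a comparison. Mean change in grade appears neither as a comparison nor as a summary.
- **General SAP rules (5.1, 5.4.1.1, 5.4.1.2).** MMRM is for continuous endpoints, and HS-PGA is not named as one. The ordinal rule reads "For the PRO endpoints with ordinal scale, the Cochran-Mantel-Haenszel (CMH) mean scores test", which is limited to patient-reported scales. HS-PGA is scored by the physician.

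**The concern.** The quantity that the protocol defines as the endpoint is never listed for comparison between arms. What is tested instead is a set of dichotomies of a six-grade scale, and these discard information. The trial is meant to explore dose effects, and the Week 16 data are to be used in planning further development (SAP 1.2 and 2.4). A less sensitive comparison of a named secondary endpoint makes it harder to see an effect or a difference between regimens. Replacing a protocol endpoint without comment also leaves the clinical study report with an unexplained departure. On multiplicity, by contrast, SAP 5.2.1 states its departure from the protocol and gives a reason.

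**Working it through.** **1. How each scale is compared between arms at Weeks 12 and 16 in the SAP**

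| Scale | Role | Comparison using the full scale? |
|---|---|---|
| mHSS (5.4.3.3.2) | secondary | yes, change from baseline |
| IHS4 (5.4.3.6.1.2) | exploratory | yes, change from baseline |
| PGI-s (5.4.3.5.7.2) | secondary | yes, distribution |
| PGA-ISD (5.4.3.6.3.2) | exploratory | yes, distribution |
| HS-PGA (5.4.3.4.2) | secondary | no, responder cuts only |

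PGA-ISD is the nearest relative, a physician scale graded 0 to 5. It is only exploratory, yet it gets the fuller comparison.

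**2. What the cuts leave out, using the grades in SAP 5.4.3.4.1 and the third cut**

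- Entry at moderate (3): must reach minimal (1), with no abscess, draining fistula or inflammatory nodule.
- Entry at severe (4): must reach mild (2).
- Entry at very severe (5): must gain three grades, because 5 to 3 is still above 2.
- Entry at mild (2): possible with 3 or 4 inflammatory nodules only, since eligibility needs a count of at least 3. Must reach clear (0).

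Gains of 5 to 4, 4 to 3 and 3 to 2 count in none of the three cuts. A gain of 2 to 1 does count in the clear-or-minimal cut, if the two-grade condition is read as attached to the third cut only. Worsening counts in none.

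**3. The plan's own figure**

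The only power statement is for HiSCR, Arm 1 against Arm 3: "Assuming a positive HiSCR score is achieved in 60% of intent-to-treat (ITT) patients" on weekly bermekimab "versus 30% in placebo treated patients (Treatment Arm 3"), with "approximately 80% power at a 0.05 significance level using a 2-sided Pearson chi-square test".

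n = [1.96 √(2 × 0.45 × 0.55) + 0.8416 √(0.24 + 0.21)]² / 0.30² = (1.379 + 0.565)² / 0.09 ≈ 42 per arm.

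This reproduces "for a randomization ratio of 1:1:1, a sample size of 126 patients (42 in each treatment group) is required" and gives 80.0% power. At 150/3 = 50 per arm, power is 86.6%. Nothing comparable is stated for HS-PGA, so steps 4 to 6 rest on assumptions.

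**4. Normal-shift model, 50 per arm, two-sided 0.05**

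- Power of mean change = Φ(d √(50/2) − 1.96).
- A cut with placebo rate p0 has active rate Φ(z(p0) + d), tested by chi-square.
- d = z(0.60) − z(0.30) = 0.253 + 0.524 = 0.78 carries over the HiSCR effect. d = 0.56 is the shift at which mean change has 80% power.

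| Placebo rate of the cut | 2% | 5% | 10% | 15% | 20% | 30% |
|---|---|---|---|---|---|---|
| d = 0.78 (mean change 97%) | 40% | 59% | 74% | 80% | 84% | 87% |
| d = 0.56 (mean change 80%) | 21% | 33% | 44% | 51% | 55% | 59% |

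Every cut loses power, but the loss runs from 97 − 87 = 10 points to 80 − 21 = 59 points, depending on the assumed rate and shift.

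**5. Simulated grades 0 to 5**

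With 42 and 50 per arm and several assumed baseline mixes, spreads and effects, baseline-adjusted mean grade at one visit stood in for the MMRM, against an unstratified chi-square on each cut. Power relative to the mean comparison:

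- clear: 0.04 to 0.61
- clear or minimal: 0.25 to 0.75
- mild or better with a two-grade gain: 0.44 to 0.86

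**6. Simulated lesion counts scored into grades, 50 per arm, HiSCR set to 30% and 60%**

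- Eight settings with 16% discontinuation: clear 8–42%, clear or minimal 19–48%, third cut 37–62%, baseline-adjusted change 77–90%. The third cut kept 0.47 to 0.69 of the power.
- A variant with between-patient log-SD of 0.8 or 1.3 and 0% or 16% discontinuation: third cut 32–51% and 56–70% respectively, unadjusted mean change 78–91%. Its lowest setting kept at most 32/78 = 0.41, slightly below the range in step 5.

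The 16% is 1 − 126/150. The protocol states no dropout rate, and the extra patients are also there for safety data. The wording of the moderate grade is not cleanly legible, so these runs needed a reconstruction of it.

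**The case against.** **The protocol's commitment is loose.** Its MMRM list includes HiSCR, which is binary, and PGI-c, which already rates change, so it cannot apply literally to every item. The section also allows further responder analyses and leaves full details to the SAP. This stands as permission to add responder cuts. It does not say that the change comparison may be dropped.

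**Ordered global scales are handled categorically throughout.** PGA-ISD and PGI-s also lose their change-from-baseline comparison, and PGI-c is only summarised. This stands: HS-PGA is not alone in departing from change from baseline. But PGA-ISD and PGI-s keep a distribution comparison, and HS-PGA has neither.

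**A real effect would be seen elsewhere.** HS-PGA is built from lesion counts, and the SAP already compares change in AN count, abscesses, draining fistulas and inflammatory nodules, plus mHSS and IHS4. This stands and limits the consequence. It does not supply the comparison of the named endpoint.

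**The general MMRM rule may be meant to cover HS-PGA.** Possibly. Sections 5.4.1.1 and 5.4.1.2 do not say so, and the HS-PGA section lists nothing of the kind. If that is the intention, one line settles it.

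**Stronger readings.** A reader might infer that the cuts roughly halve the power of this endpoint. Some assumed settings give that, but others lose much less or much more, and the documents hold no HS-PGA input to choose between them. A reader might also infer that one-grade gains carry no information at all. The 2 to 1 gain counts in the clear-or-minimal cut, and one-grade improvement is summarised over time.

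**Conclusion.** The mismatch is established from the text. The protocol's HS-PGA endpoint is change from baseline by MMRM, the SAP compares arms on responder cuts only, no other SAP rule clearly restores the change comparison, and no reason is given.

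The direction of the consequence is also clear under shift-type models: each cut has less power than an analysis of change. Its size is not derivable. Under the assumed models the third cut keeps about 0.44 to 0.86 of the power of the change analysis, with one lesion-count setting slightly lower, and the clear and clear-or-minimal cuts usually keep less. If the effect were concentrated in a few strong responders, a cut could lose less than these models show. The shift and grade models also leave out dropout and the zero-improvement rule after treatment discontinuation, and none of the calculations uses stratified tests or the repeated-measures gain of an MMRM.

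No confirmatory claim is at risk, because SAP 5.2.1 makes secondary p-values nominal and HS-PGA was never powered. This should be corrected, but it does not threaten the trial's main conclusion.

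**What to change.** Add to SAP 5.4.3.4.2, ahead of the responder bullets: change from baseline in HS-PGA grade (0 to 5) at Weeks 12 and 16, each bermekimab group against placebo, by the MMRM of Section 5.4.1.1. Add a CMH mean scores test on the grade change, stratified by prior biologic use and screening Hurley stage, as a check that does not lean on the model. Keep the three responder comparisons as supportive. If the sponsor prefers responder cuts alone, the SAP should record that the protocol's comparison was dropped, and why.

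The cost is one bullet and one table. The grades are already derived and both methods are already in the SAP. The downsides are one more nominal comparison and the treatment of six ordered grades as scores, which the protocol already accepts by naming HS-PGA for MMRM.

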## 5.4.3.5. Patient Reported Outcome

## 5.4.3.5.1. Numerical Rating Scale (NRS) for Pain and Itch [take home diary]

## 5.4.3.5.1.1. Definition

Patients will be given a diary to complete each night before bed. Patients will be asked to report "average pain", and "worst moment pain" as well as "average itch" and "worst moment itch" on a 0-10 numeric rating scale. Patient diaries will be collected weekly. A higher score indicates more severe disease (0 indicate no itch or no pain). Both pain and itch rating scale will be averaged into

a weekly score respectively (ie 7 days [from day -7 to -1] prior to a visit). Four days out of 7 days (either consecutive or nonconsecutive) are necessary to derive a weekly score; otherwise data are considered missing for that week. The baseline is defined as the average score of last 7 days prior to Week 0 study agent administration. Similarly, If there are more than 3 days missing data, then baseline is set as missing. Missing baseline will not be imputed.

• NRS30 for numerical rating pain score (weekly average): at least 30% reduction from baseline in numerical rating scale for pain.

## 5.4.3.5.1.2. Analysis Related to NRS (Pain & Itch) Score

- Proportion of participants who achieved NRS30 for pain score at worst (weekly average) at Week 12 and Week 16 among participants with baseline NRS pain score  $\geq$  3 will be compared between each of the bermekimab groups and the placebo group respectively.
- Proportion of participants who achieved NRS30 for pain score on average (weekly average) at Week 12 and Week 16 among participants with baseline NRS pain score ≥ 3 will be compared between each of the bermekimab groups and the placebo group respectively.
- Proportion of participants who achieved NRS30 at worst (weekly average) and on average (weekly average) will be summarized over time by treatment group among participants with baseline NRS score ≥ 3 respectively.
- Proportion of participants who achieve ≥3-point and ≥4-point improvement (reduction) in NRS itch score at worst (weekly average) from baseline at Week 12 and Week 16 will be compared between each bermekimab group and the placebo group among participants with baseline NRS itch score ≥ 3 and ≥4 respectively.
- Proportion of participants who achieve ≥3-point and ≥4-point improvement (reduction) in NRS itch score on average (weekly average) from baseline at Week 12 and Week 16 will be compared between each bermekimab group and the placebo group among participants with baseline NRS itch score ≥ 3 and ≥4 respectively.
- Proportion of participants who achieve ≥3-point and ≥4-point improvement (reduction) in NRS itch score at worst (weekly average) and on average (weekly average) from baseline will be summarized over time by treatment group among participants with baseline NRS itch score ≥ 3 and ≥ 4 respectively.
- Change from baseline in NRS pain score and itch score at worst (weekly average) at Week 12 and Week 16 will be compared between each of the bermekimab groups and the placebo group respectively.
- Change from baseline in NRS pain score and itch score on average (weekly average) at Week 12 and Week 16 will be compared between each of the bermekimab groups and the placebo group respectively.
- Change from baseline in NRS pain and itch score -at worst (weekly average) and on average (weekly average) will be summarized over time by treatment group.

